1.3.3 Monitoring and evaluation

Ovulation testing: Subjects will be provided with Clearblue® Fertility Tests (Inverness Medical Innovations, Inc., Waltham, Massachusetts) for use beginning between days 8-10 of the menstrual cycle (depending on individual cycle length history) and continuing daily for up to 15 days or until the LH surge is detected. The device reports a positive result on detection of the LH surge which should occur approximately 24-36 hours prior to ovulation.

Collection of samples: At each visit where we are collecting data, blood samples and mucus samples will be collected. For blood samples, approximately 5 ml of blood will be collected and sent for analysis. A basic gynecological exam will be used to collect cervical mucus. An unlubricated speculum will be placed so that the cervix will be fully visualized. A large dry sterile swab used to clean the ectocervix of any debris. We will obtain fresh mucus using a special endocervical aspirator (Unimar Aspirette device, Cooper Surgical, Trumbull, CT, USA)[58]. Grasping ring forceps will be used for collecting thick or densely adherent

endocervical mucus. For the days we are collecting endocervical cells for RNA analysis, following mucus collection, an endocervical brush will be inserted into the os and then immediately rinsed into a special RNA preserving reagent. Mucus will be transported in the collection device to a laboratory area close by where analysis will be conducted. Brush samples and any remaining mucus will immediately be frozen for later analysis.

Five collections will be performed during the natural cycle between days 3-5 (early follicular), 8-10 (mid follicular), 11-13 (late follicular), within 24 hours of positive ovulation test (ovulation), and days 6-9 post ovulation (mid luteal) (see Table 3).

Figure 3 shows the sample collection during the second part of experiments when we replace hormone exogenously. The patient will undergo 4 periods of sample collection each spanning a 24 hours period. The subject upon initiation of the randomized intervention (estradiol withdrawal vs. NET). Each collection period will include six samples (see figure 4). This sampling schedule will take place over 2 days. Beginning in the morning, we will collect samples at time 0 (initiation of intervention), 2,4, and 6 hours. They will then return the next morning for collections at 22 and 24 hours. There will also be one sample collection at the beginning of the period (3 weeks after the Lupron shot), to confirm that ovarian suppression has been achieved and mucus is poor.

This means there will be 5 collections in the natural cycle and 4 (interventions) x 6 (collections/intervention) + 1 (prior to start of period) for a total of 30 collections. These will occur over 15 visits. Enrollment can also be combined with the first collection visit to make 14 total visits). Measure outcomes are further described below.

Study Month	-	Month 1					Month 2										
		Screening	Enrollment	Natural Cycle				Lupron Injection	Ovarian Suppression	Randomized Cycles							
EF	MF			LF	Ovulation	ML	24 hr collection			24 hr collection		24 hr collection		24 hr collection			
0	1			2	3	4	5	6		7	8*	9**	10*	11**	12*	13**	14*
Consent	X																
Medical History	X																
Urine Pregnancy Test	X																
Vitals (Blood Pressure, Pulse)	X																
Height and Weight	X																
Serum Progesterone+ Estrogen Levels	X		X	X	X	X	X	X	X*	X**	X*	X**	X*	X**	X*	X**	X**
Cervical Mucus Scoring			X	X	X	X	X		X*	X**	X*	X**	X*	X**	X*	X**	X**
Sperm Penetration Testing@					X	X	X		X*	X**	X*	X**	X*	X**	X*	X**	X**
Endocervical cell collection for RNA testing			X	X	X	X	X		X*	X**	X*	X**	X*	X**	X*	X**	X**
Receive Home Fertility Test Kit		X															
Receive Study Diary		X															
Receive Combined Oral Contraceptive (at end of visit)																	X
Lupron or equivalent Injection							X										
Receive Study Patches																	
Receive Progesterone Pills																	
Receive NET									X#		X#		X#		X#		
Study wrap-up																	
Estimated time	90 m	30 m	15 m	15 m	15 m	15 m	30m	15m	8hr	2.5hr	8hr	8hr	2.5hr	8hr	2.5hr	2.5hr	2.5hr

* Visits 8, 10, 12, and 14 will include serum hormone levels, cervical mucus scoring, sperm penetration testing at 0,2,4,6 hours. Endocervical sampling will be done at 6 hours.

** Visits 9, 11, 13, and 15 will include serum hormone levels, cervical mucus scoring, sperm penetration testing at 22 and 24 hours (from previous day). Endocervical sampling will be done at 24 hours.

You will be randomized to receive NET at 2 out of the 4 24 hr visits (visits 8, 10, 12, and 14).

@ Sperm Penetration Testing is an experiment done in a laboratory where donor sperm is placed in extracted cervical mucus and evaluated for their ability to swim.

Please note the protocol will have certain flexibility regarding initiation of certain parts of the study in order to minimize study burden on the subjects. Enrollment (visit 2) and the first collection (visit 3) can be combined for one longer visit if the subject desires. During both natural and artificial cycles, a personalized study schedule regarding hormone replacement plan and sampling dates will be given to the patient. A study diary will be kept by the patient recording all medications taken by the patient as well as the daily results of the home fertility test. Almost all sampling visits have a 3-day window during the natural cycle except days marking

ovulation in the natural cycle. Similarly, the time between interventions is flexible as long as they are at least 5 days apart and the subject is able to come for back-to-back days of the 24-hour collections in the replacement cycle. Recognizing that the 24-hour samplings are time consuming and potentially burdensome, this gives flexibility to the subject on when these days occur. Also, as this is well within the three-month suppression period of leuprolide, offering this flexibility should not be a problem.

Moreover, cycles themselves can be initiated with some flexibility. Following leuprolide administration, the artificial cycle can begin between 21 to 28 days later allowing for subsequent visits to occur on weekdays or times best suited for the subject.

Cervical Mucus Testing: During and following the collection, the clinical measures of Mucus Scoring, Slide Testing and Penetration Testing will be evaluated as outlined by #1, #2 and #3 below. The remaining mucus as well the endocervical brush sample will be frozen for laboratory evaluations at later time (#4, #5, and #6). In order to prevent disruption of sperm-mucus penetration tests, sexually active women will be asked to use non-spermicidal condoms for vaginal intercourse. The women’s health research unit will provide such condoms to subjects.

1. Cervical Mucus Scoring

During and immediately following every mucus collection, these metrics will be graded: volume, consistency, cellularity, spinnbarkeit and ferning. This scoring system is described in the WHO laboratory Manual for the Examination and Processing of Human Semen and is a modification of the original Inslar Score. Table 5 below outlines the components and grading of the score. A score of 10 is considered to be conceptive mucus favoring sperm penetration.

Table 5 WHO Laboratory Scoring of Cervical Mucus

Score:	0	1	2	3
Volume- as estimated by amount that fills collection catheter	0 ml	.01-.1 ml	.1-.29 ml	= > .3 ml
Viscosity	thick, highly viscous, premenstrual mucus	mucus of intermediate viscosity	mildly viscous mucus	watery, minimally viscous, mucus
Ferning	no crystallization	atypical fern formation	primary and secondary stem ferning	tertiary and quaternary stem ferning
Spinnbarkeit	<1cm	1–4cm	5–8cm	9cm or more
Cellularity	>20 cells per HPF or >1000 cells per Pl	11–20 cells per HPF or 501–1000 cells per Pl	1–10 cells per HPF or 1–500 cells per Pl	0 cells

2. Simplified Slide Test

For both the SST and sperm-cervical mucus penetration test, cryopreserved sperm derived from our sperm bank at OHSU will be unfrozen and confirmed for activation.. Prethaw sperm count, motility and morphology sufficient for fertilization will be documented prior to use. Following thaw we will re-evaluate sperm count and motility.

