1.3.1 Subject Selection

A prospective cohort of healthy, normally menstruating women will be recruited. No subpopulations of women will be specifically included or excluded, and no special classes of subjects will be enrolled. For detailed inclusion/exclusion criteria see Table 1.

Table 1: Inclusion and Exclusion Criteria

Inclusion Criteria	Exclusion Criteria

 • Normal menstrual cycles of 25-35 days in length for at least previous 3 cycles • 21-40 years of age • BMI >18, <35 • Serum P₄ ≥ 3 ng/ml on single sample collected between days 18-25 of self-reported menstrual cycle • Flexible schedule allowing blood draws on less than 48 hour notice • In good general health • Commit to using non-hormonal contraceptive methods without spermicide during study period except those prescribed in the experimental protocol • No objections to taking study drugs • No objections to refraining from intercourse the night before any sampling and willing to using condoms during vaginal intercourse. 	
 • Oral contraceptive use or other hormone supplement within the preceding 2 months • Women with current cervical infection • Evidence of abnormal cervical cytology • Use of any IUD for contraception • Long-acting hormonal contraceptive use in the past 12 months (e.g., Depo-Provera®) • Contraindications to study drugs • Current or past pregnancy within the previous 6 months or currently trying to conceive • Desiring to conceive in the next 8 months • Breastfeeding in the past 2 months • Diagnosed Diabetes or Metabolic Syndrome • Diagnosed Polycystic Ovary Syndrome • History of, or self-reported, substance abuse • Smoker • Previous infertility treatment excluding male factor issues • Use of an investigational drug within the past 2 months • History of excisional or ablative treatment procedure on cervix (ie. LEEP, Cryotherapy, Cold Knife Cone) • Current treatment for a vaginal infection such as Bacteria Vaginosis • History of Venous thromboembolism (VTE) or inherited thrombophilias

1.3.2 Treatment Cycles:

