Frozen samples of rinsed endocervical brushings in *RNAlater* (Qiagen) will be thawed for quantitative real-time PCR. After total RNA is isolated and purified, it will be reverse transcribed into cDNA using primers. Primers for PGRMC1 and PGRMC2, mPR α and β , and PGR will be created using Primer Express software [Applied Biosystems (ABI), Foster City, CA, USA]. The primer and probe sequences for PGRMC1 and PGRMC2 have been validated recently in the macaque ovary by comparing the values obtained from real-time PCR with microarray data[61]. Transcript levels in each sample will be quantified against a five-point standard curve. Samples from similar points in the cycle will be pooled. The real-time PCRs will be performed in MicroAmp Fast Optical 96-well plates on an ABI 7500 Fast Real-time PCR System.

5. Mucus Rheological Characteristics

Once mucus samples have been evaluated by mucus score and sperm penetration (#2 and #3 above), the remaining, de-identified samples will be sent to the Complex Fluids and Soft Solids Laboratory at Oregon State University. OSU will only receive samples that are de-identified and coded by the subject number so that their tests and analysis can be correlated to serum hormone levels and results from #2-3 above. Labels on the samples will contain the subject number, the sample number (visit number) and the date the sample was originally obtained. The data returned would both be aggregated data of samples pooled from similar time points as well as data sorted by subject in order to account for inter-subject variability. OSU will use the same coding system as OHSU (subject number).

Led by [name], the lab specializes in developing both theoretical and experimental methods to study complex fluids, soft solids, miscible fluid interactions, and biological systems. They will use both sheer and extensional rheological techniques to provide detailed mechanical characterization of the cervical mucus samples. These will be performed on samples that are otherwise destroyed and will be destroyed following testing. This mechanical data will be correlated to conventional mucus scores.

6. Ion Content

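### The late-follicular sample is fixed at cycle days 11-13 for women with 25-35 day cycles, and no rule stages it by the LH surge before RT-PCR pooling

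*Combined protocol and SAP*

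**What the plan says.** - **Late-follicular visit.** Table 3 (section 1.3.2) and the text of section 1.3.3, Monitoring and evaluation, agree on cycle days "11-13 (late follicular").
- **Eligibility.** Table 1 (section 1.3.1) admits women with "Normal menstrual cycles of 25-35 days in length for at least previous 3 cycles".
- **LH test.** Section 1.3.2 says the kits are supplied to place both the late-follicular point and ovulation. Section 1.3.3 has them "for use beginning between days 8-10 of the menstrual cycle", the start depending on the woman's cycle-length history, and "continuing daily for up to 15 days or until the LH surge is detected". The surge is put at "approximately 24-36 hours prior to ovulation". Only the ovulation and mid-luteal visits are tied to the test result.
- **Pooling.** For RT-PCR (section 1.3.3, item 4): "Samples from similar points in the cycle will be pooled". The plan does not define which points count as similar. Section 1.3.10 then analyses log-transformed PCR data by one-way analysis of variance with a mixed-model routine.
- **Two internal mismatches.** Mid follicular is days 7-9 in Table 3 but days 8-10 in the text of section 1.3.3. Mid luteal is counted from the LH surge in Table 3, but the text has "days 6-9 post ovulation (mid luteal").

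**The concern.** What a late-follicular sample represents depends on its distance from the LH surge, not on the calendar day. The protocol's summary says mucus changes progressively as estrogen rises and that ovulation brings endogenous progesterone. Section 1.6 concedes that results can be affected when the point in the cycle is not known. A fixed calendar window across a 10-day range of cycle lengths (35 - 25 = 10) therefore puts different hormonal states under one label. The stated purpose of the LH test and the sampling schedule do not meet.

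Two aims in section 1.1.2 are exposed. The natural cycle is the reference for validating the artificial cycle (first aim under the primary objective). It also supplies samples for the question whether E2 and P4 regulate the membrane receptors (secondary objective). With ten women planned and 70% completion expected (10 x 0.70 = 7), one mis-staged sample is one in seven to one in ten of its group. If RNA from different women is physically combined, the mis-staging cannot be corrected afterwards.

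**Working it through.** The plan gives no figure for this point to reproduce. The check is day arithmetic.

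**Inputs**
- Sampling window: days 11 to 13 (Table 3; section 1.3.3).
- Cycle length L: 25 to 35 days (Table 1).
- Surge to ovulation: 24-36 h, that is 1.0 to 1.5 days (section 1.3.3).
- Luteal length T: **an assumption, not in the documents**. Central value 14 days, range 12 to 16.

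**Formulas**
- Ovulation day = L - T.
- Surge day = L - T - 1.5 to L - T - 1.0.
- Earliest offset from surge = 11 - (L - T - 1.0). Latest offset = 13 - (L - T - 1.5). Negative means before the surge.

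**At T = 14**
- L = 25: ovulation day 11, surge day 9.5-10. Offsets 11 - 10 = +1.0 to 13 - 9.5 = +3.5. The whole window is after the surge.
- L = 28: ovulation day 14, surge day 12.5-13. Offsets 11 - 13 = -2.0 to 13 - 12.5 = +0.5. The window straddles the surge.
- L = 35: ovulation day 21, surge day 19.5-20. Offsets 11 - 20 = -9.0 to 13 - 19.5 = -6.5. The whole window is well before the surge.

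The window is wholly after the surge at 25 days, touches or straddles it at 26-28 days, and is wholly before it at 29-35 days.

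**Sensitivity to T (days from surge)**

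| T | 25-day cycle | 35-day cycle | Cycle lengths in which the window reaches or passes the surge |
|---|---|---|---|
| 12 | -1.0 to +1.5 | -11.0 to -8.5 | 25-26 |
| 13 | 0.0 to +2.5 | -10.0 to -7.5 | 25-27 |
| 14 | +1.0 to +3.5 | -9.0 to -6.5 | 25-28 |
| 15 | +2.0 to +4.5 | -8.0 to -5.5 | 25-29 |
| 16 | +3.0 to +5.5 | -7.0 to -4.5 | 25-30 |

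At every T, the label covers samples on both sides of the surge.

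**Check without a luteal assumption.** LH testing can start as early as day 8. If it starts on day 10 and runs for 15 daily tests, the last is on day 10 + 14 = 24. Surges on days 8 to 24 would give offsets from 11 - 24 = -13 to 13 - 8 = +5. This is what the testing schedule allows for, not a forecast.

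**Mismatches.** The two mid-follicular windows differ by one day. The two mid-luteal anchors differ by 1.0 to 1.5 days, on the protocol's own interval.

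**The case against.** The strongest reply is that the plan already holds what is needed to stage samples. Section 1.3.2 names the late-follicular point as a target of the LH test. Section 1.3.3 gives each woman a personalized schedule, a window of about three days and a diary of daily test results. Section 1.3.8 measures LH, FSH, E2 and P4. When testing catches a surge before day 11, it is known before the late-follicular visit. This stands as far as the data go, and it is why the remedy is cheap. It does not remove the point: nothing moves days 11-13 by cycle length, and nothing requires these data to be used before pooling.

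A reader might also infer more than the documents support:

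- **That calendar-labelled samples are certain to be pooled irreversibly.** Item 4 speaks of similar cycle points, not of the calendar label, and does not say whether pooling is within or across women. A mixed model on the PCR data makes one pooled value per phase doubtful. Rheology data come back sorted by subject as well as aggregated, and no pooling is stated for mucus scores or penetration tests. Irreversibility applies at most to RT-PCR, on one reading.
- **That a span of -11 to +5.5 days is to be expected.** It joins a 35-day cycle with a 12-day luteal phase to a 25-day cycle with a 16-day one. Both luteal lengths are assumptions.
- **That every short cycle is sampled after the surge.** At T = 12, even a 25-day window starts one day before it. How many enrolled women have short cycles is not known.
- **That the trial's main comparison is harmed.** The primary analysis in section 1.3.10 compares the two interventions in suppressed women, and section 1.3.11 calls the randomized cycles the most critical data. That section plans no test of the late-follicular sample against the artificial cycle. The natural counterpart of the mid-cycle patch level, the ovulation sample, is already anchored to the LH test.

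**Conclusion.** The point holds, at minor severity. The written schedule mis-stages some natural-cycle samples, and it is not reconciled with the stated purpose of the LH test. With an assumed 14-day luteal phase, one label runs from 9 days before to 3.5 days after the surge. For any luteal length from 12 to 16 days, it still crosses the surge. Sampling on or after the surge is confined to short cycles, about 25-28 days at the central assumption.

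The consequence is limited to the natural-cycle reference and the secondary receptor objective. Permanent loss is a risk only for RT-PCR material, and only if samples are combined across women before staging. The norethindrone versus estrogen-withdrawal comparison is untouched. The mid-follicular and mid-luteal mismatches are small wording inconsistencies that need reconciling in their own right.

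**What to change.** 1. **Stage before pooling.** Before RT-PCR pooling, and in all natural-cycle summaries, assign phase by days from the detected LH surge, supported by the serum LH, E2 and P4 already measured. Do not label or pool as late follicular any sample taken on or after the surge. Define in the same place what counts as a similar point for pooling.
2. **Schedule by cycle length.** For remaining subjects, set the late-follicular visit from cycle-length history, as is already done for the start of LH testing. Keep it distinct from the mid-follicular visit, since moving it earlier in short cycles could make the two collide.
3. **Earlier subjects.** Section 1.3.11 keeps the 7 women already enrolled on the previous protocol, whose schedule is not shown. Apply the same staging to them where an LH date and hormone values exist and their RNA has not been pooled.
4. **Reconcile** the mid-follicular window and the mid-luteal anchor between Table 3 and the text of section 1.3.3.

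**Cost.** Scheduling and labelling text only, with no added visits, samples or assays. The real downside is that some women may end up with no late-follicular sample, so that group may shrink, which is noticeable with about ten women. The number staged out should be reported.

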1.1.2 Objectives and hypothesis

Hypothesis: Contraceptive action of progestogens occur through direct effects on cervical mucus and not indirectly through reduction in systemic estrogen.

Primary Objective: Using ovarian suppressed women, we seek to individually evaluate the effect of E_2 and progestin on cervical mucus to better understand its hormonal regulation. To do this we will:

1. Create and validate an artificial model of the menstrual cycle using exogenous E_2 and P_4 replacement in ovarian suppressed women.
2. Evaluate effects of increasing estrogen levels on cervical mucus.
3. Evaluate the timing of both the onset, duration and termination of progestin actions on cervical mucus following estrogen priming.
4. Compare the effects of estrogen withdrawal to the synthetic progestin norethindrone.

Secondary Objectives:

1. To determine if membrane bound progesterone receptors are present in the cervix and are regulated by E_2 / P_4 .

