The study will begin with the first day of menstruation following enrollment. This cycle will be untreated but monitored and sampled (see figure 2 and section 1.3.3 for sample collection schedule). In order to determine points corresponding to late follicular and ovulation in these women, subjects will be provided with Clearblue® Ovulation Test (Inverness Medical Innovations, Inc., Waltham, Massachusetts). The fertility monitors test for urinary metabolites of LH, which will aid in staging of the menstrual cycle. At the end of the natural cycle treatment (menses), subjects will receive the gonadotropin releasing hormone (GnRH) agonist Lupron® (leuprolide acetate; Abbvie, Chicago, IL) in a 11.25 mg single injection which is sufficient for 3 months of continuous suppression. At 3 weeks, a visit will occur where an additional blood aliquot will be obtained and sent to the endocrine lab to confirm suppression. A phone call following confirmation will be made to instruct the subject to begin patches. We have previous experience with this model that shows ovarian suppression is reliably achieved at 21 days[48]. After confirmation of ovarian suppression and collection of baseline serum samples, all subjects will undergo replacement of endogenous estrogen with patches.

Transdermal E₂ patches changed twice weekly (Vivelle-Dot®, Noven Pharmaceuticals Inc.; Miami, FL) will be used to replace E₂, with a 0.1 mg/day transdermal dose having been previously shown to restore circulating E₂ levels in ovarian-suppressed women to 89 ± 38

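### The schedule table omits the mucus sample at the Ovarian Suppression visit that the text of section 1.3.3 requires, so following the table loses the only mucus taken under suppression before estrogen add-back

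*Combined protocol and SAP*

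**What the plan says.** Four places in the combined protocol and SAP bear on this visit.

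- **Section 1.3.3, Monitoring and evaluation, text.** One collection is placed three weeks after the leuprolide injection, "to confirm that ovarian suppression has been achieved and mucus is poor". It is the last term in the count of "4 (interventions) x 6 (collections/intervention) + 1 (prior to start of period) for a total of 30 collections", where the other five come from the natural cycle. The general rule earlier in the section is: "At each visit where we are collecting data, blood samples and mucus samples will be collected".
- **Section 1.3.3, schedule table.** In the Ovarian Suppression column the row "Serum Progesterone+ Estrogen Levels" carries a mark. The rows for mucus scoring, sperm penetration and endocervical cells are blank there.
- **Section 1.3.2, Treatment Cycles.** "At 3 weeks, a visit will occur where an additional blood aliquot will be obtained and sent to the endocrine lab to confirm suppression". After a phone call the woman starts patches: "After confirmation of ovarian suppression and collection of baseline serum samples, all subjects will undergo replacement of endogenous estrogen with patches". Mucus is not mentioned.
- **Section 1.1.2, objectives.** Objective 1 is to create and validate the artificial cycle in suppressed women. Objective 2 is: "Evaluate effects of increasing estrogen levels on cervical mucus".

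**The concern.** The text gives the visit two purposes, hormonal suppression and poor mucus. The table provides for only the first. Staff who work from the table, with section 1.3.2 doing nothing to correct them, would draw blood, telephone the woman and start patches.

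The sample cannot be recovered later. Section 1.3.2 keeps women on 0.1 mg/day patches between interventions and raises them to 0.3 mg/day the day before each one. Every later time-0 sample is therefore taken after estrogen priming, and no mucus is scheduled at the 0.1 mg/day level. The suppression visit is the one scheduled point where mucus can be seen with ovarian hormones suppressed and nothing yet replaced.

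That sample shows whether suppression reached the cervix as well as the serum. It is also the starting point for saying that replaced estrogen turned poor mucus into fertile mucus, which is what objectives 1 and 2 need in the artificial cycle.

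**Working it through.** **1. Reproduce the stated count.** From the text: 5 natural-cycle collections + 4 interventions × 6 + 1 suppression visit = 5 + 24 + 1 = 30. This matches the stated total exactly.

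**2. Locate the visit in the table.** The table header is broken in extraction, and the sampling rows have 17 cells for 16 visits (0 to 15). Two anchors fix the columns. The norethindrone marks fall in cells 9, 11, 13 and 15, which are visits 8, 10, 12 and 14, as the footnote says. The first starred sampling mark is in cell 9 (visit 8). Cell 8 is therefore visit 7, Ovarian Suppression. In cell 8:

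| Row | Visit 7 |
|---|---|
| Serum progesterone and estrogen | X |
| Cervical mucus scoring | blank |
| Sperm penetration testing | blank |
| Endocervical cells | blank |

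The footnotes do not restore the sample. They list mucus work only for visits 8 to 15.

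**3. Count mucus collections from the table.** One star means four time points (0, 2, 4, 6 h) and two stars mean two (22, 24 h). The surplus 17th cell is ignored, because the footnote names only visits 9, 11, 13 and 15 for the two-star mark.

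- Natural cycle: 5
- Visits 8, 10, 12, 14: 4 × 4 = 16
- Visits 9, 11, 13, 15: 4 × 2 = 8
- Visit 7: 0
- Total: 5 + 16 + 8 + 0 = 29

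That is one short of 30. Marking mucus at visit 7 restores 30.

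**4. Cross-check against payment** (section on Subject Recruitment and Compensation: $45 per collection, $250 for the injection, $100 per 24-hour period, $2,000 in all).

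- 30 collections: 30 × 45 + 250 + 4 × 100 = 1,350 + 250 + 400 = $2,000
- 29 collections: 29 × 45 + 250 + 4 × 100 = 1,305 + 250 + 400 = $1,955

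The total fits 30, so the visit is budgeted as a collection. This does not prove that mucus is included, since a blood-only visit could be paid as well.

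**5. Look for a substitute sample.** Natural-cycle samples carry endogenous hormones. Time-0 samples are on 0.3 mg/day. The nearest candidate is the end of an estrogen-withdrawal period. Section 1.3.2 gives a patch half-life of 5.9 to 7.7 without a unit; hours are assumed here. The fraction left at 24 h is 0.5^(24/5.9) = 0.060 to 0.5^(24/7.7) = 0.115, or about 6% to 12%. Those samples follow priming and are outcome samples, so they do not replace an unprimed baseline.

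**6. Size of the affected group** (section 1.3.11). Ten were planned and 7 are enrolled under the original protocol: 10 − 7 = 3 on the amended schedule, if ten is total enrolment.

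**The case against.** The best defence is that the text already settles the matter. The general rule requires blood and mucus wherever data are collected, and the text counts this visit as a collection. Section 1.3.2 does not exclude mucus, and its additional aliquot can be read as blood on top of the usual samples. Blanks in this table are also weak evidence. As extracted, the rows for patches, progesterone pills and study wrap-up carry no mark at any visit, although patches and progesterone are clearly given. Figure 3, cited for the sampling plan, is not available and may show the sample. All of this is fair. It makes the table the likely error, and the table still needs correcting.

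Several stronger readings are tempting, and the documents do not support them.

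- A reader might take the 15-minute slot as a sign that the visit is blood-only or too short. Natural-cycle visits 2 to 5 also have 15 minutes and are marked for mucus scoring, so the slot shows nothing.
- A reader might infer that the receptor-expression objective loses its hormone-free brush. Neither the text nor the table clearly plans a brush at this visit, so that loss does not follow from the mismatch.
- A reader might infer that no estrogen contrast would remain. The withdrawal periods give mucus and serum as estrogen falls, and the natural cycle gives them across the follicular rise.
- A reader might infer that objectives 1 and 2 fail for the whole study. Seven women follow the original protocol, whose sampling is not described here, and section 1.3.11 says no more data are needed from its middle artificial cycle.

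**Conclusion.** The inconsistency is real and specific. The text requires 30 collections, including one meant to show poor mucus under suppression, while the table schedules 29 mucus collections and leaves that one out. Following the table would cost each affected woman her only mucus sample under suppression before add-back, and with it the check on the suppressed state and the unprimed baseline for objectives 1 and 2 in the amended cycle.

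The reach is limited. The randomized norethindrone-versus-withdrawal comparison does not use this sample. About 3 women are exposed, on the assumption that ten is total enrolment. The conclusion also rests on the column alignment in the working, which both the norethindrone marks and the footnotes support. With so few women on the amended schedule, each lost baseline matters, and the correction is worth making before the next suppression visit.

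**What to change.** - In the schedule table, mark cervical mucus scoring at the Ovarian Suppression visit, before patches start.
- Identify the visit by name as well as number. The numbering is not stable: the flexibility paragraph in section 1.3.3 calls enrollment visit 2 where the table has visit 1, and section 1.3.5 refers to a visit 17 that the table does not contain.
- In section 1.3.2, add mucus to the sentence that now names only a blood aliquot at three weeks.
- State whether sperm penetration testing and an endocervical brush apply at this visit. Reconciling the passages does not require either.

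This changes one table column and one sentence. The cost to the participant is a mucus exam at a visit already counted as a collection, and the stated payment total already fits 30 collections.
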